2.2 Secondary objectives

To demonstrate that the proportion of patients experiencing intolerable drug-related adverse events is lower with a low than a standard dose.

To demonstrate that health-related quality of life (HRQOL) and satisfaction with treatment score higher with a low than a standard dose.

To demonstrate that, on a societal perspective, the treatment of newly diagnosed epilepsy with low AED doses will translate into savings in terms of contacts with the National Health System (in- and outpatient visits, drug expenditures).

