3.4 Randomization

After informed consent, eligible patients will be randomized to receive a low or a standard dose of the assigned drug. Randomization will be centralized at the Istituto Mario Negri IRCCS, Milano. Randomization sequence will be created using SAS 9.4 (SAS Institute, Cary, NC, USA) statistical software and will be stratified by center with a 1:1 allocation using random block sizes of 4. Each center will receive randomization scratch-cards.

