3.5 Data collection at baseline and during follow-up

The following variables will be collected at admission by the evaluating physician: date of birth, sex, height, weight, arterial blood pressure, heart rate, family history of epilepsy, history of febrile seizures, date of onset of seizures, seizure type(s), epilepsy syndrome or non-syndromic epilepsy, neurological and psychiatric examination (coded as normal or abnormal), first interictal EEG (coded as normal, slow or epileptiform), imaging findings (coded as normal or abnormal for seizure etiology), relevant comorbidities, concurrent treatments, HRQOL (using the Italian version of the QOLIE-31 inventory; Beghi et al, 2005), patient satisfaction (PSQ-18), laboratory examinations if available (CBC, alanine aminotransferase, aspartate aminotransferase, gamma glutamyltranspeptidase, creatinine, alkaline phosphatase, calcium, phosphorus, sodium, potassium, ammonia, amylase). Each patient will be followed for 12 months. In the follow-up visits the same laboratory tests will be performed as per clinical practice or caring physician discretion, including the AED plasma concentration assay. Ad-hoc diaries will be given to each patient and/or caregiver for the collection of follow-up data. The diaries will include the number of seizures (with dates) and the type and severity of adverse events (with dates, outcome and actions). To preserve blindness, daily intake and timing of the assigned, but not the daily dose, will be recorded in the diaries. Any contact with the National Health System for the management of seizures and AEDs will be also noted in the diaries with dates. The contents of the diaries will be verified during each telephone contact by the evaluating physician and by the treating physician at the time of the face-to-face visits.

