6.7 Study drugs dispensation

This is a not-for-profit study, according to Health Ministry Decree 17.12.2004. The same decree certifies that study drug costs are covered by the national health service (Art 2) in case of not-for-profit studies and if the study drug is used as per marketing authorization.

In this study, the drugs will be dispensed by the hospital pharmacies. When the patient receives the information on the drug and the daily dose assigned by randomization, he/she (or the treating physician) will contact the center's pharmacist to obtain the assigned drug. The drug will be reimbursed according to the directives imparted by each Italian region (eg, File F). Drugs will be labeled by pharmacists according to Vol 4 GMP, Annex 13, Labelling. All used (empty) and unused drug will be returned in the provided packaging to the investigator's staff for drug accountability. After being verified by the Clinical Monitor, all unused drug will be destroyed at the centre.

7. Visit schedule and assessments (see Study Flow Chart)

The recruitment period will last for 12 months and enrolled patients will be followed for 12 months after randomization. Enrolled patients will undergo periodic visits with a predetermined schedule:

7.1 Baseline evaluation.

The following assessments will be accomplished:

- a. Verification of all inclusion and exclusion criteria
- b. Recording of demographic data and clinical parameters: date of birth, sex, height, weight, arterial blood pressure and heart rate.
- c. Physical, neurological and psychiatric examination
- d. General clinical history: concomitant diseases and medications
- e. Assessment of birth control methods for women in childbearing age
- f. Family history of epilepsy, history of febrile seizures, date of onset, type of seizures, seizure

frequency at onset, epileptic syndrome or non-syndromic epilepsy

- g. Administration of the QOLIE-31 and PSQ-18 inventories
- h. Results of first interictal EEG
- i. Results of available blood sample withdrawal
- j. Imaging findings (MRI or CT scan as per clinical indication)
- k. Randomization and assignment of allocated treatment
- l. Delivery of seizure diary
- m. Appointment for the next visit at the discretion of the caring physician. First telephone contact at 4 weeks.

7.2 Follow-up visits.

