7.7 Scales and e-CRF

The QOLIE-31 inventory will be used at the baseline and last visit to measure HRQOL (Annex QOLIE-31). The Patient Satisfaction Questionnaire will be used at the baseline and last visit to measure patient's satisfaction (Annex PSQ-18).

The e-CRF used for the collection of demographic and clinical data is appended (Annex Case Report Form).

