10.4 Outcome measures, statistical methods and data analysis

Expected outcomes are the following:

1. compared to patients assigned to standard daily doses, patients receiving low daily doses of AEDs are expected to incur in similar rates of seizure recurrence;
2. compared to patients assigned to standard daily doses, patients receiving low daily doses of AEDs are expected to undergo significantly less treatment changes due to intolerable drug-related adverse events;
3. compared to patients assigned to standard daily doses, patients receiving low daily doses of AEDs are expected to experience less drug-related intolerable adverse events;
4. compared to patients assigned to standard daily doses, patients receiving low daily doses of AEDs are expected to experience a better quality of life;
5. the National Health System is expected to incur in significant savings with low daily doses of AEDs.

Primary outcome

The proportion of patients experiencing a treatment failure motivated by the need to change the assigned dose or the assigned drug for seizure relapse during the follow-up.

Secondary outcomes

1. the proportion of patients experiencing a treatment failure motivated by intolerable drug-related adverse events during the follow-up;
2. QOLIE-31 total score at the last visit;
3. the score of the seven PSQ-18 subscales (general satisfaction, technical quality, interpersonal manner, communication, financial aspects, time spent with doctor, accessibility and convenience) at the last visit;
4. the mean daily patient's cost of health care resources consumed for the management of epilepsy during the first 12 months of the study.

Descriptive statistics will be provided for all the data collected at admission, comparing the two

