treatment regimens. Numerical variables will be described using means, standard deviations, medians and ranges, while categorical variables using frequencies and percentages. The proportion of patients experiencing the primary end-point over the entire follow-up will be estimated using Kaplan-Meier survival curves. The difference between the two treatment arms in the proportion of patients experiencing the primary endpoint, with 95% confidence intervals (95% CI), will be calculated at 1, 3, 6, 9 and 12 months, and compared to the non-inferiority margin (m). In presence of variables at admission having a different distribution in the two treatment groups and that could have an effect on treatment response (possible confounders), a multivariable analysis will be also performed using a Cox's proportional hazards model, adjusted for these variables. A hazard ratio (HR), with the corresponding 95% CI, will be reported, and compared to a relative risk (RR) obtained considering as reference the proportion of patients experiencing the primary endpoint in the standard dose arm (p_0) and taking into account the non-inferiority margin ($RR=(p_0+m)/p_0$). The secondary end-point will be evaluated using Kaplan-Meier survival curves, comparing the two treatment arms with the log-rank test. In presence of possible confounders with a different distribution in the two treatment arms at baseline, a Cox's proportional hazards model will be used. The QOLIE-31 total score, the seven PSQ-18 subscales scores at the last visit, and mean daily patient's costs will be compared, separately, between treatment arms using the t-test, the Wilcoxon-Mann-Whitney test, or a multivariable linear regression model. Subgroup analyses will be performed separately for sex, age groups, drug, seizure types (focal/focal-to-bilateral), etiology (known/unknown), and center.

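### QOLIE-31, PSQ-18 and cost: Section 10.4 offers three methods without naming a main one or any covariates, and specifies no baseline adjustment although both scales are collected at baseline

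*Combined protocol and SAP*

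**What the plan says.** Section 2.2 makes these outcomes confirmatory in tone: "To demonstrate that health-related quality of life (HRQOL) and satisfaction with treatment score higher with a low than a standard dose". It also sets out to show savings for the health service.

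Both instruments are measured twice. Section 3.5 lists HRQOL and patient satisfaction among the variables taken at admission, Section 7.1 includes "g. Administration of the QOLIE-31 and PSQ-18 inventories", and Section 7.7 states: "The QOLIE-31 inventory will be used at the baseline and last visit to measure HRQOL" and "The Patient Satisfaction Questionnaire will be used at the baseline and last visit to measure patient's satisfaction". The flow chart agrees.

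Section 10.4 defines the HRQOL outcome as "QOLIE-31 total score at the last visit". The PSQ-18 outcome is likewise the seven subscale scores at the last visit, and the cost outcome is mean daily cost over the first 12 months. One sentence gives the analysis of all nine: they "will be compared, separately, between treatment arms using the t-test, the Wilcoxon-Mann-Whitney test, or a multivariable linear regression model". The only stated use of the baseline scores is the general descriptive comparison of admission data between arms.

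Section 3.4 says that randomization "will be stratified by center with a 1:1 allocation using random block sizes of 4". In 10.4, centre appears only as a subgroup factor.

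**The concern.** Two things are left open.

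First, the three methods are alternatives with no order among them and no condition for choosing. The same section gives a trigger for its Cox models (baseline imbalance in a possible confounder), but attaches none to the linear regression. Several p-values could exist for each outcome, and the plan does not say which one decides. For cost, the methods also answer different questions. The t-test and linear regression compare means; the Wilcoxon-Mann-Whitney test compares ranks. Savings depend on the mean, and with skewed costs the methods can disagree.

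Second, the baseline score of each scale is already collected, and it is the natural covariate for the same score at follow-up. The t-test and Wilcoxon test cannot use it. The regression could, but its covariates are not listed. Because the sample size rests on the primary endpoint alone (Section 10.6), precision on these outcomes has to come from the analysis.

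At stake are power on secondary objectives that the trial says it will demonstrate, and the credibility of whichever test is reported.

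**Working it through.** **Plan's own figure.** Section 10.6 gives 168 per arm for non-inferiority with 60% seizure-free in both arms, one-sided 0.025 and 80% power. At the 15-point margin, n = (1.960 + 0.842)² × 2 × 0.6 × 0.4 / 0.15² = 167.4, so 168. With 10% dropout, 336 / 0.9 = 373.3, so 374. Both figures reproduce. They concern the primary endpoint; the plan gives no figure for QOLIE-31, PSQ-18 or cost.

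**Assumptions not in the documents.** Two-sided 0.05 for each secondary outcome; baseline-to-follow-up correlation r of 0.3 to 0.7, with 0.1 as a low case; a true difference of 0.25 SD.

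**Number evaluable.** The documents allow two readings. Sections 7.7 and 10.4 speak of the last visit. Sections 2.4 and 7.2 place the scores at 12 months, while patients leave the study at relapse or at a treatment change for adverse events (7.2), with a final visit within 72 hours after relapse (6.6, 7.4). If last-visit scores count, 168 per arm may hold. If only 12-month scores count, the 60% assumed seizure-free leave 0.60 × 168 = 100.8, about 101 per arm, before adverse-event exits.

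**Variance.** Adjusting for baseline multiplies the variance of the arm difference by 1 - r²: 0.91, 0.75 and 0.51 at r = 0.3, 0.5 and 0.7. This factor does not depend on n.

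**Power.** Power = Φ( d / √[(2/n)(1 - r²)] - 1.96 ), with d = 0.25.

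| Evaluable per arm | Unadjusted | r = 0.3 | r = 0.5 | r = 0.7 |
|---|---|---|---|---|
| 168 | 63% | 67% | 75% | 89% |
| 101 | 43% | 46% | 54% | 70% |

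Example, n = 168 and r = 0.5: √(2/168) = 0.1091; 0.1091 × √0.75 = 0.0945; 0.25 / 0.0945 - 1.96 = 0.686; Φ = 0.754. At r = 0.1 and n = 168 power is 63.4% against 63.0% unadjusted, a gain of under one point.

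**Detectable difference.** With 168 per arm, the difference detectable with 80% power is (1.960 + 0.842) × √(2/168) = 0.306 SD unadjusted, and 0.292, 0.265 or 0.218 SD adjusted at r = 0.3, 0.5 or 0.7. With 101 per arm the unadjusted figure is 0.39 SD.

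**Open choice of test.** Null trials were simulated with 168 per arm (10,000 per setting, Monte Carlo standard error about 0.002 to 0.003), taking the smaller p-value of the t-test and the Wilcoxon test. False-positive rates were 6.0 to 6.3% for normal scores, 6.4 to 6.9% for moderately skewed scores (log-normal, log-SD 0.5), and 7.7 to 7.9% for strongly skewed, cost-like data (log-SD 1). Each test alone stayed near 5%.

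**The case against.** The strongest reply is that a conventional reading is available: t-test or Wilcoxon according to distribution, and regression when a confounder is imbalanced. A multivariable regression has covariates by definition, and the baseline scores are admission variables, so nothing excludes them. This stands in part. A reader might infer that the plan discards the baseline scores; the documents do not support that. They support only that no adjustment is specified. Writing the conventional rule down, with covariates named, would remove the ambiguity, but it would not by itself secure the precision gain.

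A second reply is that power figures at 168 per arm assume every patient has a usable score. That is fair, and is why the 101-per-arm row is shown. If last-visit scores are used instead, scores taken within days of a seizure mix with 12-month scores, and a single r for all patients is then only approximate. The direction of the gain is unaffected.

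A third is that the false-positive excess is small. That also stands: it is one to three points, as an upper bound, and assumes that the test is chosen after seeing the results. A reader might quote a higher rate for picking the best of all three methods, but that calculation needs a baseline-adjusted regression, which the plan does not specify.

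**Conclusion.** The point holds, as a gap in specification for secondary endpoints. Section 10.4 fixes neither the main method nor the covariates for nine comparisons, and specifies no baseline adjustment for scores measured at baseline. Cost has no baseline value, so only the choice of method is at issue there.

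The size depends on a correlation that the documents do not give. The variance reduction is 9% at r = 0.3, 25% at 0.5 and 49% at 0.7, whatever the number evaluable, and close to nothing at r = 0.1. Absolute power depends further on the assumed 0.25 SD and on whether about 168 or about 101 per arm are evaluable. The possible false-positive rate is at most about 6 to 8% per outcome.

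A reader might infer that the looseness reaches the primary result. It does not: the Kaplan-Meier difference is compared with the non-inferiority margin without condition, and the log-rank test for the adverse-event endpoint is also stated without condition. The change is worth making because it uses data already collected.

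**What to change.** In Section 10.4, before any comparative data are seen:

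- **QOLIE-31 total and each PSQ-18 subscale.** Make ANCOVA the single main analysis, with treatment arm, the baseline value of the same score, and centre (the stratification factor) as terms. Pool small centres by a rule stated in advance. Keep the Wilcoxon-Mann-Whitney test as a sensitivity analysis only.
- **Mean daily cost.** Name one mean-based main method, for example the difference in arithmetic means with a bootstrap 95% confidence interval. Any rank-based comparison is supportive.
- **Which score.** State whether the analysed score is the 12-month or the last-visit one, so that the number evaluable is clear.

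The cost is a few sentences, a pooling rule for small centres and a little programming. No new data, visits or patients are needed. ANCOVA and the bootstrap are not the only acceptable choices; what matters is that one main method per outcome is fixed and that the baseline score is used where it exists.

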standard doses but carry a significantly lower risk of adverse effects, are associated with a better quality of life and satisfaction, and translate into significant savings for the National Health System. The study can help define the lowest effective therapeutic strategy and, if possible, the lowest effective dose for each AED.

2. Study objectives

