10.6 Sample size calculation

The sample size is based on the primary efficacy end-point. The non-inferiority margin is a relative 20% difference, as stipulated by the ILAE, up to a maximum of an absolute 15% difference between the two dosing schedules for the primary endpoint. Assuming a one-sided p of 0.025 and that the proportion of patients who will not have a seizure in the low dose and standard dose groups is 60%, 168 patients per group provides 80% power to test whether a low AED dose is non-inferior

to a standard dose. Assuming 10% drop-out rate, the required sample size will be 374 patients.

11 Administrative procedures

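### Section 10.4 plans subgroup analyses for six factors, including drug and center, with no interaction test and no rule for interpretation, and uses center, the only randomization stratum, only as a subgroup

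*Combined protocol and SAP*

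**What the plan says.** The whole subgroup plan is the last sentence of section 10.4: "Subgroup analyses will be performed separately for sex, age groups, drug, seizure types (focal/focal-to-bilateral), etiology (known/unknown), and center". Neither that section nor any other gives an interaction test, an exploratory label, a minimum subgroup size, a rule for pooling sparse levels or a rule for reading the results.

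For the primary endpoint, section 10.4 compares the arm difference and its 95% CI with the non-inferiority margin. If baseline variables are unbalanced, it adds a Cox model whose hazard ratio is compared with a relative risk derived from the margin. Center appears in neither analysis.

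Section 3.4 says that randomization "will be stratified by center with a 1:1 allocation using random block sizes of 4". Drug is not a stratum: section 6 leaves the choice to the caring physician and lists nine drugs with a low and a standard dose. Section 1 hopes that the study can help define, "if possible, the lowest effective dose for each AED". The objectives and endpoints in section 2 ask for no conclusion about an individual drug.

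Section 10.6 sizes only the overall comparison: "168 patients per group provides 80% power to test whether a low AED dose is non-inferior".

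**The concern.** Whether halving the dose matters more for one drug than for another is a question about the difference between drug-specific effects. A set of within-drug results does not answer it. One interval may clear a threshold and the next may not, although the two effects are fully compatible with each other. Only a direct contrast, that is, a treatment-by-drug interaction, addresses the question, and none is planned.

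At this trial's size most drug and center groups will be small. Without a rule for interpretation, nothing prevents a table of by-drug results from being read as a list of drugs for which the low dose is or is not adequate, when the pattern is noise. The hope expressed in section 1 makes that reading easy.

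The point on center is separate. It is the one factor built into the randomization, and an analysis that reflects the design would carry it as a stratum. Section 10.4 does not.

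**Working it through.** **Inputs.** From section 10.6:
- Type I error: "Assuming a one-sided p of 0.025", so z = 1.96.
- Rate in both arms: "the proportion of patients who will not have a seizure in the low dose and standard dose groups is 60" percent, so the variance term is 2 × 0.6 × 0.4 = 0.48.
- Margin: "The non-inferiority margin is a relative 20% difference, as stipulated by the ILAE, up to a maximum of an absolute 15% difference". Taken as 15 points, with 12 points (20% of 60%) as the other end of the range.
- Total: "Assuming 10% drop-out rate, the required sample size will be 374 patients".

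**Step 1: reproduce the plan.** n per arm = (1.96 + 0.842)² × 0.48 / 0.15² = 167.4, rounded up to 168. With 10% dropout, 168 / 0.9 = 186.7, rounded up to 187 per arm, 374 in total. The stated figures reproduce at 15 points. At 12 points the same formula gives 262 per arm.

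**Step 2: assumptions for subgroups.** The documents do not give these:
- The primary margin is applied within the subgroup, the true difference is 0, and the arms are equal in size within the subgroup.
- The share of patients on each drug is unknown, so a range is shown.
- The number of centers is unknown. The range 17 to 26 comes from section 1 (17 centers in the earlier trial, 26 approached in the survey).

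**Step 3: precision and chance of showing non-inferiority.** Half-width = 1.96 × √(0.48/n). Chance = Φ(margin / √(0.48/n) − 1.96). Total evaluable is 336.

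| Subgroup | n per arm | Half-width (points) | Chance, 15-point margin | Chance, 12-point margin |
|---|---|---|---|---|
| Drug with 5% of patients | 8 | 48 | 9% | 7% |
| Equal split over 9 drugs | 18.7 | 31 | 15% | 11% |
| Drug with 20% | 34 | 23 | 24% | 17% |
| Drug with 40% | 67 | 17 | 43% | 29% |
| Half the patients (e.g. one sex) | 84 | 15 | 51% | 36% |
| Drug with 60% | 101 | 14 | 59% | 41% |
| One of 17 centers | 9.9 | 43 | 10% | 8% |
| One of 26 centers | 6.5 | 53 | 8% | 6% |

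For the equal split: √(0.48/18.7) = 0.160, and 0.15/0.160 − 1.96 = −1.02, which gives 15%. The normal approximation is slightly low at these sizes. Exact binomial enumeration gives 17% (Wald interval) or 20% (Newcombe interval) at 19 per arm, and 8 to 14% at 6 to 10 per arm, which covers the center sizes. The conclusion is the same.

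**Step 4: dependence on the drug mix.** A 50% chance at 15 points needs 1.96² × 0.48 / 0.15² = 82 per arm, which is 82/168 = 49% of all patients. At most two drugs can reach that under any mix. The expected number of nine equally effective drugs that would not show non-inferiority is 9 × (1 − 0.153) = 7.6 with equal use. It is also 7.6 with an illustrative 40/15/12/10/8/5/4/3/3% mix.

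**Step 5: the contrast that matters.** With 18.7 per arm in each of two drugs, the difference between their dose effects has standard error √2 × 0.160 = 0.227 and a 95% half-width of 1.96 × 0.227 = 44 points. The interaction is the right quantity, but it too will be imprecise.

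**The case against.** A reader might infer that the plan would declare most equally effective drugs to have failed non-inferiority. The documents do not support that. Section 10.4 states the comparison with the margin for the two treatment arms overall. The subgroup sentence mentions no margin, endpoint or decision rule, and section 10.6 powers only the overall test. The figures above are therefore conditional. Even then, the accurate term is non-inferiority not shown.

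A reader might also infer that the plan has chosen within-subgroup comparisons as its method. The word separately may only mean one factor at a time. The same section uses it that way for the quality-of-life, satisfaction and cost outcomes, and on that reading an interaction model is not excluded. What stands is that no such model is stated.

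Nor does section 1 ask the subgroup analyses for drug-specific verdicts. Its sentence is hedged and does not refer to them.

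On center, stratified randomization does not make a look at consistency worthless. Section 1 reports that centers differ in dosing habits (12 opting for low doses, 7 for standard), which is a fair reason to look. Small numbers argue for descriptive reporting, not necessarily for removal.

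Finally, an interaction test over nine drugs has little power, as step 5 shows. That is true, and it is why the statement on interpretation matters as much as the test.

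**Conclusion.** The concern holds as a gap in specification. Section 10.4 names six subgroup factors with no interaction test and no rule for interpretation, and it leaves the randomization stratum out of the primary comparison and the Cox model.

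The scale of the problem rests on three assumptions: the margin is carried into subgroups, there is no true difference, and arms are balanced within each subgroup. The chance of showing non-inferiority at 15 points then runs from about 9% to 59% per drug as its share of patients goes from 5% to 60%, and is about 8 to 10% per center with 17 to 26 centers. At 12 points every figure is lower. The exact percentages depend on a drug mix and a number of centers that are not stated. That most of nine drugs would not show non-inferiority does not depend on the mix.

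The overall primary analysis is not invalidated. This is a minor point that is worth correcting because it costs little.

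**What to change.** In section 10.4:

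- Replace the separate analyses with one model per factor containing treatment, the factor and their interaction. Report the subgroup effects as exploratory estimates with 95% CIs.
- State that no non-inferiority conclusion is drawn within any drug or center.
- Use center as a stratum in the primary comparison and in the Cox model.
- Optionally, estimate the drug effects with a random-effects (shrinkage) model. A check of consistency across centers may stay as a descriptive display.

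The cost is SAP wording and a few extra models, with no added patients or visits. The interaction tests will themselves have low power across nine drugs, and the trial gives up drug-specific verdicts. It could not support these in any case: 80% power for each of nine drugs at 15 points would need 9 × 336 = 3,024 evaluable patients. The subgroup change is a cheap improvement; using center as a stratum is a free one.
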